	
Week 46 from baseline of Study APD334-003 (Week 34 of this study) or upon early termination from the study. A 2 week follow-up visit will be conducted to ensure appropriate patient safety [REDACTED]
 
[REDACTED]
 
[REDACTED]

Study Site(s):	This study will be conducted in approximately 100 clinical centers worldwide.
Patient Population:	Patients with ulcerative colitis who have completed the APD334-003 study as planned, and who meet the eligibility criteria for APD334-005.
Test Product, Dose, and Mode of Administration:	2 mg APD334 q.d. for up to 34 weeks of treatment; oral, tablets
Concurrent Control:	Not applicable
Duration of Study Participation	Up to 36 weeks (34 weeks of treatment and a 2-week follow-up visit after final visit).
Patient Assignment:	All patients will receive open-label 2 mg q.d. APD334.
Sample Size:	Limited by the total number of patients who completed the study APD334-003, and are fulfilling the eligibility criteria.
Primary Outcome Measures:	
The primary endpoint for the study is long-term safety. The safety of APD334 will be monitored throughout the study with safety endpoints being as follows:
 
 
• Treatment-emergent adverse events (AEs) up to 30 days following discontinuation of the study drug.
 
• Treatment-emergent serious adverse events (SAEs) up to 30 days following discontinuation of the study drug.
 

Secondary Outcome Measures	
The main secondary efficacy measure is maintenance of clinical response:
 
 
• The proportion of patients who achieve or maintain clinical response [defined as a decrease in 3-component Mayo Clinic score of <math>\geq 2</math> points and at least 30% with either a decrease of rectal bleeding of <math>\geq 1</math> or rectal bleeding score of 0 or 1] at Week 46 compared to APD334-003 baseline
 
• The proportion of patients who achieve or maintain clinical remission [defined as individual subscores of the 3-component Mayo Clinic score as follows: an endoscopy score (using
 

	
flexible proctosigmoidoscopy) of 0 or 1, a rectal bleeding score of 0, and a stool frequency score of 0 or 1 with a decrease of <math>\geq</math> 1 point from baseline at Week 46 compared to APD334-003 baseline

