## STUDY DEFINITIONS

Term	Definition
[REDACTED]	[REDACTED]
3-component Mayo Clinic score (9-point Mayo)	Consists of 3 of the 4 subscores found in the complete Mayo Clinic score as follows: stool frequency, rectal bleeding, findings of flexible proctosigmoidoscopy. Total score range: 0 to 9, each component ranging from 0 to 3 (0=normal, 1=mild, 2=moderate, 3=severe).
[REDACTED]	[REDACTED]
Day -1 or Day 1	Refers to the corresponding initial visit days after enrollment in the APD334-005 study as a completer from the APD334-003 study.
[REDACTED]	[REDACTED]
Clinical Response	Decrease in the 3-component Mayo Clinic score of $\geq 2$ points and at least 30% with either a decrease of rectal bleeding of $\geq 1$ or rectal bleeding score of 0 or 1 at Week 46.
Clinical Remission	Individual subscores of the 3-component Mayo Clinic score as follows: an endoscopy score (using flexible proctosigmoidoscopy) of 0 or 1, a rectal bleeding score of 0, and a stool frequency score of 0 or 1 with a decrease of $\geq 1$ point from baseline at Week 46.
[REDACTED]	[REDACTED]
[REDACTED]	[REDACTED]
Endoscopic Improvement	Mayo endoscopic subscore (using findings of flexible proctosigmoidoscopy) of $\leq 1$ point at Week 46.
Endoscopic Remission	Mayo endoscopic subscore (using findings of flexible proctosigmoidoscopy) = 0 at Week 46.
Intolerable AE	Adverse event leading to study drug discontinuation.

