### 9.6.1 Data Analysis for Secondary Efficacy Endpoints

The secondary efficacy outcome of achievement or maintenance of clinical response will be based on the proportion of patients who achieve or maintain clinical response [defined as a decrease in 3-component Mayo Clinic score of  $\geq 2$  points and at least 30% with either a decrease of rectal bleeding of  $\geq 1$  or rectal bleeding score of 0 or 1] at Week 46 compared to APD334-003 baseline using the ITT population. All patients who prematurely discontinue for any reason will be considered failures (non-responders) for all the proportion based endpoints. Similar analyses will be performed in terms of the other Week 46 proportion based endpoints such as proportion of patients achieving clinical remission and proportion of patients with endoscopic improvement.

For each study visit during the study, stool frequency and rectal bleeding subscores will be derived

- [Redacted bullet point]
- [Redacted bullet point]
- [Redacted bullet point]

All patients who prematurely discontinue for any reason will be considered failures (non-responders) for all the proportion based endpoints.

Descriptive statistics of N, mean or mean change, and standard deviation will be produced for continuous efficacy endpoints.

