### **3.2.2. Secondary Endpoints**

Secondary efficacy endpoints are achievement, durability and maintenance of clinical response and/or clinical improvement. They include the following:

- The proportion of patients who achieve clinical response at end of treatment in APD334-005; the proportion of patients who achieve clinical response at Week 12 in APD334-003 and maintain clinical response at end of treatment in APD334-005. [definition of clinical response: a patient has achieved clinical response if he/she meets criteria of clinical remission defined below, or meets criteria of clinical response i.e. a decrease in 3-component Mayo Clinic score of  $\geq 2$  points and at least 30% with either a decrease of rectal bleeding of  $\geq 1$  or rectal bleeding score of 0 or 1] at Week 46 compared to APD334-003 baseline]
- The proportion of patients who achieve clinical remission at end of treatment in APD334-005; the proportion of patients who achieve clinical remission at Week 12 in APD334-003 and also maintain clinical remission at end of treatment in APD334-005 [definition of clinical remission: individual subscores of the 3-component Mayo Clinic score as follows: an endoscopy score (using flexible proctosigmoidoscopy) of 0 or 1 (excluding friability), a rectal bleeding score of 0 or 1, and a stool frequency score of 0 or 1 with a decrease of  $\geq 1$  point] at Week 46 compared to APD334-003 baseline]

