## **4.4. Analysis Populations**

The analyses of all proportion-based and all continuous efficacy variables will use the Modified Intent-to-Treat (MITT) population as primary. In addition, all endpoints that include the endoscopy subscore will use Completers population (CP).

Analysis populations will be presented in a listing for all enrolled patients.

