### **8.1. Efficacy Assessments**

Efficacy assessments will be listed for each patient for the MITT population where relevant.

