## **8.3. Secondary Efficacy Analysis**

Secondary efficacy endpoints are listed in Section [3.2.2](#).

[figure not shown]
The secondary efficacy outcome of achievement or maintenance of clinical response will be based on the proportion of patients who achieve or maintain clinical response at end of treatment compared to APD334-003 baseline using the MITT and CP populations. Summary statistics i.e. total number of patients (N), frequencies (n), proportion (%) and its 90% CI for patients that achieved or maintained clinical response (responders) at end of treatment in APD334-005 will be produced as described in Section [4](#).

[figure not shown]
Similar summary statistical analyses will be produced for the second secondary efficacy outcome i.e. clinical remission at Week 46 compared to APD334-003 baseline.

Each secondary efficacy endpoint will be summarized, within the same presentation, by the following:

- Proportion of patients that achieved clinical response/clinical remission at Week 12 in APD334-003
- Proportion of patients that achieved clinical response/clinical remission at end of treatment in APD334-005
- Proportion of patients that achieved clinical response/clinical remission at both Week 12 in APD334-003 and end of treatment in APD334-005

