The clinical remission definition has been updated to include “a rectal bleeding score of 0 or 1” in comparison with Protocol Amendment 04 (27 Mar 2017) to be consistent with the definition in final SAP of APD334-003 study.

The clinical response definition has been updated as “a patient has achieved clinical response if he/she meets criteria of clinical remission, or meet criteria of clinical response defined in the protocol.” to be consistent with the definition in final SAP of APD334-003 study.

The following changes have been applied to the Analysis Populations to the SAP in comparison with Protocol Amendment 04 (27 Mar 2017):

- ITT population has been removed – no longer needed as APD334-005 is an open label study
- Definition of CP population has been updated to include “This CP population consists of all patients in the MITT population who completed the extension study” and “Note that CP population will be used only for endpoints that include the endoscopy subscore, unless otherwise stated.” – to be consistent with the definition in final SAP of APD334-003 study
- CP population will be used only for endpoints that include the endoscopy subscore:

[REDACTED]

Sponsor was notified that laboratory tests for five patients [REDACTED] had been sent to local labs for the purpose of safety follow up on blood cell counts after last treatment. Such follow up may still be needed at time of database lock. The local laboratory results will be translated in English and archived in study file. Sponsor will write a section in CSR to describe the findings and to assess the safety issues for these [REDACTED] patients.

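### SAP remission accepts rectal bleeding 0 or 1 where the protocol requires 0, and no readable planned summary gives the rate on the protocol's bleeding criterion

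*SAP*

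**What the plan says.** The protocol defines clinical remission in three places, each with a rectal bleeding score of 0. The Synopsis specifies "flexible proctosigmoidoscopy) of 0 or 1, a rectal bleeding score of 0, and a stool frequency score of 0 or 1". Study Definitions has "a rectal bleeding score of 0, and a stool frequency score of 0 or 1 with a decrease of" at least 1 point, and Section 9.5.1 repeats this. On the protocol's subscore scale (Study Definitions and Section 6.9.6), 0 is normal and 1 is mild.

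SAP 3.2.2 sets the endoscopy score at "of 0 or 1 (excluding friability), a rectal bleeding score of 0 or 1, and a stool frequency score of 0 or 1".

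SAP 12 lists the bleeding change against Protocol Amendment 04: "The clinical remission definition has been updated to include" a bleeding score of 0 or 1, for consistency with the final APD334-003 SAP. SAP 1 says the SAP is final before database lock.

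SAP 8.3 plans three rows for each secondary endpoint: Week 12 of APD334-003, end of treatment in APD334-005, and "Proportion of patients that achieved clinical response/clinical remission at both Week 12 in APD334-003 and end of treatment in APD334-005". SAP 14.2 assigns remission to the MITT and Completers populations. All of this uses the SAP definition.

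**The concern.** Remission is one of two secondary efficacy endpoints, and achieving and maintaining it is part of the secondary objective (Protocol 2.2). The study has no control comparison and no hypothesis test (Protocol 9.1.2), so the descriptive rate is itself the efficacy result and its definition gives it its meaning.

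A reader who knows the protocol would take a patient in clinical remission to be free of rectal bleeding. Under the SAP that need not be so, and the planned table does not show how many of the counted patients have a bleeding score of 1. The row for remission at both time points has the same difficulty. The protocol speaks of achieving or maintaining remission but does not define this two-time-point proportion, and under the SAP's rule a patient can move from bleeding 0 to bleeding 1 and still be counted.

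**Working it through.** The documents give no expected remission rate, sample size or subscore distribution, so there is no stated figure to reproduce. The check compares the two definitions.

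**Inputs.** Each subscore runs from 0 to 3 (Protocol, Study Definitions). The criteria are:

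| Component at end of treatment | Protocol | SAP 3.2.2 |
|---|---|---|
| Endoscopy | 0 or 1 | 0 or 1, with a friability exclusion |
| Rectal bleeding | 0 | 0 or 1 |
| Stool frequency | 0 or 1, with a fall of at least 1 | 0 or 1, with a fall of at least 1 |

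Two working choices apply. The fall of at least 1 point is read as a fall in stool frequency from the APD334-003 baseline. The friability wording is left out, because most of Protocol 6.9.6 is redacted and it cannot be told whether that wording changes the endoscopy criterion or restates the scoring.

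**Step 1: qualifying score combinations.** Number of combinations = endoscopy values × bleeding values × stool frequency values.

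- Baseline stool frequency 2 or 3 (end value 0 or 1 allowed):
  - SAP: 2 × 2 × 2 = 8, highest total 1 + 1 + 1 = 3 of 9.
  - Protocol bleeding criterion: 2 × 1 × 2 = 4, highest total 1 + 0 + 1 = 2.
- Baseline stool frequency 1 (end value must be 0):
  - SAP: 2 × 2 × 1 = 4, highest total 1 + 1 + 0 = 2.
  - Protocol bleeding criterion: 2 × 1 × 1 = 2, highest total 1 + 0 + 0 = 1.

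**Step 2: what is added.** For baseline stool frequency 2 or 3, the four added combinations (endoscopy, bleeding, stool frequency) are (0,1,0), (0,1,1), (1,1,0) and (1,1,1). For baseline 1 they are (0,1,0) and (1,1,0). All have bleeding exactly 1.

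**Step 3: direction and size of the gap.** On bleeding alone, the SAP set contains the protocol set. In one population of size N, therefore:

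SAP rate − bleeding-0 rate = (SAP remitters with bleeding 1) / N ≥ 0.

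The direction does not depend on how the 1-point fall is read, because both definitions carry the same condition.

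**Step 4: the row for both time points.** Take a patient with bleeding 0 at Week 12 and 1 at end of treatment, who meets the endoscopy and stool frequency criteria at both. The SAP rule counts this patient in the row. With bleeding 0 required at both times, the patient is not counted.

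**Step 5: is the bleeding-0 rate reported elsewhere?** SAP 8.3 and the readable part of 14.2 have no such row. SAP 8.1 plans listings: "Efficacy assessments will be listed for each patient for the MITT population where relevant". The rate could be rebuilt from these only if they show the subscores, which the readable text does not say.

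**The case against.** The strongest reply is that the change was made properly. It is declared in SAP 12 with a reason, in a SAP finalised before lock, and Protocol 9 leaves analysis detail to the SAP. A table that sets Week 12 of APD334-003 beside end of treatment needs one definition across both studies, and nothing in the documents obliges the sponsor to report the superseded one. All of this stands, and it supports keeping the SAP definition. It does not show how far the change moves the rate.

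The exploratory endpoints and analyses are redacted, so a bleeding-0 summary might be planned there. That also stands, and the point is limited to readable text. If such a summary exists, the sponsor need only point to it.

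The combination counts follow directly from allowing two values instead of one, and they say nothing about patients. This is correct: 8 against 4 must not be read as twice as many remitters. The counts show only direction and the score totals reached.

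An added row would not recover the protocol's analysis. This is also correct. Protocol 9.6.1 uses the ITT population and states: "All patients who prematurely discontinue for any reason will be considered failures (non-responders) for all the proportion based endpoints". The SAP dropped ITT, and Section 4.4 says: "The analyses of all proportion-based and all continuous efficacy variables will use the Modified Intent-to-Treat (MITT) population as primary". SAP 4 also carries forward the last endoscopy. The row must therefore be labelled as restoring the bleeding criterion only.

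Finally, the endpoint is descriptive, in an open-label study whose primary endpoint is safety. That limits the consequence to interpretation, but does not remove it.

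**Conclusion.** The concern holds. The SAP widens the remission bleeding criterion from 0 to 0 or 1, openly and before lock, and no readable planned summary shows the rate on the protocol's criterion. The reported remission rate, and the row for both time points, can include patients with mild bleeding.

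The size cannot be derived from the documents. What is fixed is that the bleeding-0 rate is equal to or below the SAP rate, and that the gap is the share of patients who are SAP remitters with bleeding 1. This is a statement about bleeding alone, within the same population and with the other criteria held constant. The net effect of all differences between the protocol's and the SAP's remission analyses is not determined. No test result is affected; what changes is the meaning of a secondary endpoint. The sponsor should make the addition below.

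**What to change.** Keep the definition aligned with APD334-003 as the main one. In the SAP 8.3 remission table, add a sensitivity row with rectal bleeding 0 and all other criteria unchanged. Give it at end of treatment and, to match the table's own layout, at Week 12 and at both times, for the MITT and Completers populations. Label it as restoring the protocol's bleeding criterion only, not the protocol's ITT analysis with discontinuations counted as failures. If the database is already locked, report the row in the clinical study report as a later addition, with the explanation that Protocol 9 and SAP 1 call for.

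The cost is 3 rows × 2 populations (SAP 14.2) × 6 columns (SAP 4) = 36 extra proportions with 90% confidence intervals, or 1 × 2 × 6 = 12 if only end of treatment is added. The table already needs the subscores, so no new data are collected. The drawback is a second, equal or lower, remission figure beside the first.

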### **3.2.3. Exploratory Endpoints**

### 3.3. Treatments

#### 3.3.1. Study Drug

  
Arena Pharmaceuticals will provide adequate supplies of etrasimod tablets. Etrasimod tablets will be provided as a 2 mg strength.

#### 3.3.2. Placebo

Not applicable.

Note: Under Protocol Amendment 02 (28 Sep 2015), patients that were randomized to Placebo received  tablets  that matched the active tablets in size, shape and appearance.

## 4. GENERAL STATISTICAL CONSIDERATIONS

Continuous data will be summarized using descriptive statistics (i.e., n, mean, median, standard deviation (SD), 90% confidence interval (CI) for change or percent change from baseline, minimum and maximum). For the summary statistics of all numerical variables unless otherwise specified, minimum and maximum will be displayed to the same level of precision as reported. Mean, median and 90% CIs will be displayed to one level of precision greater than the data collected. Standard deviation will be displayed to two levels of precision greater than the data collected.

For proportion-based measures, n, frequencies, proportion and its 90% CI will be produced. The denominator for all percentages will be the number of patients within the treatment group for the analysis set of interest, unless otherwise stated. Percentages will be presented to 1 decimal place. When count data are presented, the percentage will be suppressed when the count is zero in order to draw attention to the non-zero counts. A row denoted “Missing” will be included in count tabulations where specified on the shells to account for dropouts and missing values.

There is no formal between group inferential comparisons for study endpoints due to lack of control group. Summary statistics will be provided for the primary safety endpoint, secondary efficacy endpoints, exploratory efficacy endpoints, and additional safety measures. All analysis summaries will be presented as follows:

Previously Treated in APD334-003 (APD334-005 treatment: 2 mg etrasimod)				APD334-005 treatment:	APD334-005 treatment:
Placebo	1 mg etrasimod	2 mg etrasimod	1 mg & 2 mg etrasimod	2 mg etrasimod	Placebo

[figure not shown]
[figure not shown]
Listings will include a subtitle to indicate both treatments, i.e. treatment received in APD334-003 study and treatment received in APD334-005 study.

[figure not shown]
[figure not shown]
[figure not shown]
If endoscopy was performed prior to Week 46, then last observation carried forward (LOCF) imputation method will be used for the endoscopy subscore. Any endoscopy performed during the APD334-005 extension study (after Week 12 visit) will be used for LOCF imputation.

All data summaries and statistical analyses will be performed using the SAS software version 9.3 or higher (SAS Institute, Cary, NC).

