## **4.3. Randomization, Stratification, and Blinding**

### **4.3.1. Randomization and Stratification**

Not applicable for this open-label extension study.

Note: Patients that were enrolled under Protocol Amendment 02 (28 Sep 2015) were randomized to Placebo or 2 mg q.d. etrasimod and remained blinded. More details about changes in the study design are covered in Sections [1](#) and [12](#).

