## 12. CHANGES IN THE PLANNED ANALYSIS

Under Protocol Amendment 02 (28 Sep 2015) eligible responders on active treatment in the APD334-003 study (who choose to continue on to the APD334-005 study) underwent 1:1 randomization to 2 mg etrasimod q.d. or matching Placebo, while eligible Placebo responders in the APD334-003 study (who choose to continue on to the APD334-005 study) remained on Placebo. Responder patients stayed blinded. Non-responders in the APD334-003 study (who choose to continue on to the APD334-005 study) were administered with open-label 2 mg etrasimod. Under Protocol Amendment 03 (20 Oct 2016) eligible patients (who choose to continue on to the APD334-005 study) must have completed the APD334-003 study and were administered open-label 2 mg etrasimod. Data gathered on patients before Protocol Amendment 03 will follow the Protocol Amendment 03 analyses and data presentation as described in this SAP document. Patients that received 2mg etrasimod under any Protocol Amendment will be pooled into a 2 mg etrasimod group and patients that received placebo prior to Protocol Amendment 03 will be included in a second group. All listings will be presented by these two treatment groups, namely 2 mg etrasimod and Placebo, and by treatment previously received in APD334-003 study.

The following exploratory objectives have been added to the SAP in comparison with Protocol Amendment 04 (27 Mar 2017) to be consistent with the objectives in the APD334-003 study:

[REDACTED]

The following exploratory endpoints have been added to the SAP in comparison with Protocol Amendment 04 (27 Mar 2017) to be consistent with the endpoints in the APD334-003 study:

[REDACTED]

The following exploratory endpoints have been removed from the SAP in comparison with Protocol Amendment 04 (27 Mar 2017), as these are no longer needed:

[REDACTED]

The following subgroup analysis has been added to the SAP in comparison with Protocol Amendment 04 (27 Mar 2017):

[REDACTED]

The following subgroup analyses have been removed from the SAP in comparison with Protocol Amendment 04 (27 Mar 2017), as these have been already evaluated in APD334-003 study and are no longer needed:

[REDACTED]

The 95% CIs have been changed to 90% CIs for all analyses in comparison with Protocol Amendment 04 (27 Mar 2017) to be consistent with the APD334-003 study.

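### SAP Section 4 cites the lack of a control group, but the Amendment 02 responders it also analyses were randomised 1:1 to 2 mg or placebo, and no visible planned summary shows those arms as randomised

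*SAP*

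**What the plan says.** SAP Section 4 gives the rule and its reason: "There is no formal between group inferential comparisons for study endpoints due to lack of control group". Protocol 9.1.2 gives the same reason for having no hypothesis tests. The column layout in SAP Section 4 nevertheless includes a placebo column for APD334-005 treatment.

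SAP Section 12 explains where that column comes from. Under Amendment 02:

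- APD334-003 responders on active treatment "underwent 1:1 randomization to 2 mg etrasimod q.d. or matching Placebo", and "Responder patients stayed blinded".
- "eligible Placebo responders in the APD334-003 study (who choose to continue on to the APD334-005 study) remained on Placebo"; these patients were not randomised.
- Non-responders "were administered with open-label 2 mg etrasimod".

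SAP Section 4.3.1 confirms that patients enrolled under Amendment 02 "were randomized to Placebo or 2 mg q.d. etrasimod and remained blinded". Section 3.1 adds that their final assessment was at Week 52 rather than Week 46.

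Section 12 then sets the grouping. On the active side, "Patients that received 2mg etrasimod under any Protocol Amendment will be pooled into a 2 mg etrasimod group". Everyone given placebo in the extension, whether randomised to it or continuing on it, forms the other group. The Section 4 columns split the 2 mg patients by APD334-003 treatment. They do not split them by randomised or open-label status, response at entry, or amendment. The placebo column is not split. SAP Section 8.3 reports response and remission at Week 12, at end of treatment, and at both, within these columns.

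**The concern.** The stated reason is incomplete. It describes the current design but not every patient in the analysis. For the Amendment 02 responders there was a concurrent, blinded, randomised placebo arm.

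The secondary objective covers both achieving and maintaining response or remission. A single-arm proportion cannot separate maintenance due to the drug from response that would have persisted anyway. The Amendment 02 subset is the only part of this study with a randomised comparison on that question. If it appears only inside pooled columns, a reader of the tables has just the 2 mg and placebo columns to set side by side, and those differ in who was put into them as well as in treatment.

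**Working it through.** The documents state no sample size, power or expected rate, so there is no figure to reproduce. The check is where each kind of patient lands, followed by illustrations on assumed rates.

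**1. Column membership (SAP Sections 4 and 12)**

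| Patients | Assignment in APD334-005 | Summary column |
|---|---|---|
| Amendment 02, active-treatment responders, 2 mg | Randomised, blinded | 2 mg total, and prior 1 mg or 2 mg |
| Amendment 02, active-treatment responders, placebo | Randomised, blinded | Placebo |
| Amendment 02, placebo responders | Continued on placebo, not randomised | Placebo |
| Amendment 02, non-responders | Open-label 2 mg | 2 mg total, and prior-treatment column |
| Amendment 03 and 04 enrolees | Open-label 2 mg | 2 mg total, and prior-treatment column |

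The first two rows are the randomised contrast. No column holds either row alone. The combined prior 1 mg and 2 mg column does not recover it, because that column also holds open-label patients and its only comparator is the mixed placebo column.

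**2. Effect on the maintenance row (response at both Week 12 and end of treatment)**

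Unless otherwise stated, the denominator is everyone in the treatment group within the analysis set (SAP Section 4). Under Section 12 the placebo column contains only APD334-003 responders, while the 2 mg column includes non-responders, who cannot maintain a response they did not have. This assumes that response status at entry agrees with the SAP definition.

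Assume 60% of randomised 2 mg patients and 30% of all placebo-column patients maintain response. Add k Week 12 non-responders per randomised 2 mg patient, and leave later enrolees out. The 2 mg column then reads 0.60/(1 + k):

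- k = 0.5: 0.60/1.5 = 40%, against 30% on placebo
- k = 1: 0.60/2 = 30%, against 30%
- k = 2: 0.60/3 = 20%, against 30%

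An assumed randomised difference of +30 points reads as +10, 0 or −10. A larger sample with the same mix would not change this.

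**3. Effect on the end-of-treatment row**

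Here non-responders can count as successes, so the distortion can go either way. Assume 10 randomised per arm, with 70% on 2 mg and 40% on placebo (+30 points). Add 40 to 80 other 2 mg patients at 30% to 70%, and 5 to 10 placebo continuers at 20% to 60%. The extremes of the combinations tried are:

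- Low: (10×0.7 + 80×0.3)/90 = 34.4%; (10×0.4 + 10×0.6)/20 = 50.0%; difference about −16 points
- High: (10×0.7 + 80×0.7)/90 = 70.0%; (10×0.4 + 10×0.2)/20 = 30.0%; difference +40 points

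**4. Precision of the randomised contrast**

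For n per arm at 60% v 30%, the approximate (Wald) 90% half-width is 1.645 × √(0.6×0.4/n + 0.3×0.7/n) = 1.645 × √(0.45/n):

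| n per arm | Half-width (points) |
|---|---|
| 5 | 49 |
| 10 | 35 |
| 20 | 25 |
| 30 | 20 |

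At 5 per arm only 5×0.3 = 1.5 placebo successes are expected, so the Wald figure is a rough guide and the report should use a small-sample interval. For scale, 80% power at two-sided 0.05 for these rates needs [1.96√(2×0.45×0.55) + 0.842√0.45]²/0.30² ≈ 42 per arm.

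**The case against.** The strongest reply is that the choice is deliberate and disclosed. Amendment 03 removed the hypotheses, the power calculation and the between-group differences. SAP Section 12 says openly that earlier patients will follow the Amendment 03 presentation. The primary objective is long-term safety. Only formal comparison is excluded, and with a handful of patients per arm an interval of ±35 to ±49 points would say little. This stands as a reason for no hypothesis test. It does not make the stated reason correct for the Amendment 02 patients, and small numbers would have been the better reason to give.

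A reader might go further and infer that the randomised evidence has been lost. The documents do not support that. Listings are to be presented by both APD334-005 and APD334-003 treatment. Placebo patients with prior active treatment are, under Section 12, the randomised placebo arm. The 2 mg arm also needs Week 12 response and enrolling amendment to be identified. Nor can absence from the plan be asserted outright: Section 12 reports an added subgroup analysis whose content is redacted, Section 8.5 is not visible, and parts of Section 4 are not shown.

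A reader might also infer that the randomised subset gives an unbiased answer as it stands. It would not under the SAP's MITT rule, which requires a post-enrolment measurement for each endpoint and so could break the balance if dropout differs by arm. Prior active treatment also includes 1 mg, so the 2 mg arm mixes patients continuing their dose with patients whose dose changed.

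Finally, the denominator may be set differently in table shells that are not visible. Restricting it to Week 12 responders would remove the distortion in step 2. The columns would still mix randomised and non-randomised patients.

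**Conclusion.** The concern holds in this form. The reason given in SAP Section 4 is true of the Amendment 03 and 04 design and not of the Amendment 02 patients analysed under the same SAP. In the visible text no planned summary isolates the randomised contrast, and the pooled 2 mg and placebo columns are not comparable for maintenance of response.

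The size cannot be fixed from the documents, which give neither the number randomised nor any rates. On the assumptions above, the columns can hide or reverse a 30-point randomised difference in maintenance, and can misstate a 30-point end-of-treatment difference in either direction. These figures show that the columns cannot stand in for the randomised comparison; they do not estimate the actual bias.

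It would also be wrong to read Section 4.3.1 as meaning that the whole placebo column is a randomised control. Section 12 shows that it also holds placebo responders who were never randomised.

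**What to change.** 1. In SAP Section 4, replace the reason. Say that the current design has no control group, that a randomised placebo arm exists for Amendment 02 active-treatment responders, and that no formal test is planned.
2. Unless the redacted subgroup analysis already does this, add one descriptive table limited to APD334-003 active-treatment responders randomised under Amendment 02:
   - all randomised and dosed patients, by randomised arm;
   - patients who discontinue early or have no end-of-treatment assessment counted as non-responders (Protocol 9.6.1 already covers premature discontinuation; the missing-assessment part is an extension of it);
   - the time point stated as end of treatment, Week 52 for these patients;
   - prior 1 mg or 2 mg treatment shown;
   - counts for maintained response, maintained remission and TEAEs, with the risk difference and a small-sample interval (Newcombe or exact), labelled descriptive and without a hypothesis test.
3. Show the never-randomised placebo continuers separately, and keep all other tables.

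The cost is a wording change and one table from data already collected. The downside is that the interval may be wide if few patients were randomised.
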